1.0 Study Summary

Study Title	Improving Healthy Lifestyle Behaviors in Midlife Black
	Women to Lower Heart Disease Risk.
Study Design	Developmental research study and pilot.
Primary Objective	The primary objective of this research is to develop a midlife
	Black women's Stress-reduction WELLness
	intervention, B-SWELL , for midlife Black women based on
	the stressors and themes identified in the PI's preliminary
	research.
Secondary	Determine the feasibility of the B-SWELL intervention with
Objective(s)	a trial of 50 midlife Black women randomized
	to the B-SWELL intervention (25) or to a wellness education
	(WE) control group (25):
Research	8-week community-based, behavioral intervention
Intervention(s)/	
Investigational	
Agent(s)	
IND/IDE #	N/A
Study Population	Midlife Black women
Sample Size	50
Study Duration for	8 weeks
individual	
participants	
Study Specific	B-SWELL: Black women's Stress-reduction WELLness
Abbreviations/	Intervention
Definitions	WE: Wellness attention control group
	CBPR: Community-Based Participatory Research
	C-RAB: Community Research Advisory Board

2.0 Objectives*

2.1 Describe the purpose, **specific aims**, or objectives.

Purpose: The purpose of this research is to develop a midlife **B**lack women's **Stress**-reduction **WELL**ness intervention, **B-SWELL**, to promote healthy lifestyle behaviors based on the stressors and themes identified in the PI's preliminary research and consistent with the American Heart Association's *Life Simple 7 Success Plan (LS7) behaviors*.

Aim 1: Develop the B-SWELL intervention for midlife Black women through the innovative leveraging of CBPR methodology and LS7 modifiable healthy lifestyle behaviors.

- a) To develop components of the B-SWELL intervention prototype for midlife Black women.
- b) Obtain ratings of the new components of the B-SWELL from an expert panel consisting of four midlife Black women laypersons, three researchers and three integrative health care specialists for degree of accuracy, relevance, and feasibility to inform further refinements.

Aim 2: Determine the feasibility of the B-SWELL intervention with a trial of 50 midlife Black women randomized to the B-SWELL intervention (25) or to a wellness education (WE) control group (25):

- a) Obtain recruitment, retention, treatment fidelity ratings, and satisfaction ratings for the intervention procedures for both groups, including technology;
- b) Compare mediator measures (stress, self-efficacy) for participants in the B-SWELL intervention group with those in the WE group at 8 and 12 weeks.
- c) Compare outcome measures (LS7 summary scores, unhealthy days, general health, depressive symptoms) for participants in the B-SWELL intervention group with those in the WE attention control group at 8 and 12 weeks.
- 2.2 State the hypotheses to be tested.

Our hypothesis proposes that B-SWELL (intervention) participants will show improved self-efficacy in managing life stress and adopting the LS7 behaviors, compared to an attention control group (WE group) receiving traditional wellness education.

3.0 Background*

3.1 Describe the relevant prior experience and gaps in current knowledge.

Cardiovascular disease (CVD) is the primary cause of death in all women, and as women transition through midlife, the prevalence of CVD exceeds that of men.(American Heart Association, 2016) Midlife Black women, defined as ages 40-64, unduly shoulder the burden of CVD (49%), hypertension (40%), and heart failure (50% greater risk).(Go et al., 2013; Gudmundsdottir, Hoieggen, Stenehjem, Waldum, & Os, 2012) Midlife Black women also report higher levels of chronic stress and greater numbers of stressful life events in comparison to midlife White women,(Schulz et al., 2000; Turner & Avison, 2003) putting them at greater risk for CVD. In addition to the physical impact, coping with chronic stress takes time and energy away from selfcare, functioning as a barrier to the adoption of healthy lifestyle behaviors.(Pedersen, von Kanel, Tully, & Denollet, 2017; Pogosova et al., 2015) Existent interventions do not fully address the unique factors contributing to the experience of stress, lifestyle behaviors, and CVD risk in midlife Black women.

In the PI's prior research, we identified the particularities of stress and how they manifest in the lives of midlife Black women. Key stressors included: workplace stress, parenting, finances, and media stress.(Jones, Sternberg, Janson, & Lee, 2016; H. J. Jones, Norwood, & Bankston, 2018) The theme, 'Strong Black Woman', was identified along with the subthemes of 'gendered racism and discrimination' and 'life balance'.(H. J. Jones et al., 2018) The Strong Black Woman persona explains the elevated risk for morbidity and persistent chronic stress in Black women due to simultaneous exposures to racism and sexism and the gendered expectations of being the primary familial care-giver and supporter of others and the community alike.(Mullings, 2000; Woods-

Giscombe, Lobel, Zimmer, Wiley Cene, & Corbie-Smith, 2015) This persona serves as a coping mechanism under extremely oppressive conditions, cultivating strength and resilience among Black women, but leads to a deterioration of health due to chronic active coping.(Geronimus, 2001; Lekan, 2009)

Many Black women internalize characteristics of the 'Strong Black Woman' and while these characteristics are generally positive, it is easy to envision how a 'Strong Black Woman' can become stressed, overwhelmed, and isolated.(Beauboeuf-Lafontant, 2009) Much research has been done to provide a voice and understanding to the Black female experience in America however, none have used that voice to identify and target the unique perceived stressors that may serve as barriers to the adoption of healthy lifestyle behaviors. The purpose of this research proposal is to develop a midlife Black women's Stress-reduction WELLness intervention, **B-SWELL**, to promote healthy lifestyle behaviors based on the stressors and themes identified in preliminary research. (Jones et al., 2016; H. J. Jones et al., 2018) Community-based participatory research (CBPR) methods will be used to engage the community and include midlife Black women in the development of the B-SWELL. We propose that the skills and knowledge gained through participation in the B-SWELL program will increase receptivity to the healthy lifestyle behaviors outlined in the American Heart Association's Life Simple 7 Success Plan (LS7). The LS7 targets seven risk factors known to increase cardiovascular related health risk: cholesterol, fasting glucose, blood pressure, body mass index, physical activity, diet, and smoking.(Windham et al., 2017) By the age of 40, the prevalence of CVD is equal between men and women but by the age of 60, more women are affected. (Mozaffarian et al., 2016) This noted increased risk of CVD across midlife warrants the need for intervention.

3.2 Describe any relevant preliminary data.

Two preliminary studies conducted by the PI will inform this research. (Jones et al., 2016; H. J. Jones et al., 2018) These studies sought to understand the complexity of stress as a health indicator for midlife Black women. The first study used mixed methods to assess changes in perceived stress across midlife and identify significant life stressors. (Jones et al., 2016) The sample of 15 midlife Black women from the San Francisco Bay area (mean age 61years) had high-perceived stress scores that persisted across midlife. Although stress scores were consistent over time (between ages 40 and 60), the sources of stress changed. Significant life stressors included finances, caring for family members, relationships, personal health and aging, race and gender-based discrimination, and raising children. (Jones et al., 2016)

"Race is the hidden in plain view stressor in USA life. I am Black and that has caused me stress working in a White world. Equal, or perhaps worse, is the fight to have my voice heard as a woman."

This sample of midlife Black women was part of a larger cohort of Black and White midlife women. In the cohort (N=39), midlife Black women had higher perceived stress scores, a greater number of depressive symptoms and, were more likely to be obese and have elevated blood pressures compared to White women of similar age and demographics.(Jones et al., 2016) Higher perceived stress scores correlated with older biological age, indicating a greater health risk profile;¹⁹ a finding that is consistent with the literature.

The second study conducted by the PI(H. J. Jones et al., 2018) used community engagement and focus groups to identify stress-related themes in the lives of midlife Black women residing in the Greater Cincinnati area. Key stressors were identified within six major themes: workplace, parenting, finances, social media, gendered racism and discrimination, and life imbalance(H. J. Jones et al., 2018). The participants also identified stress-reduction strategies and barriers to adopting those strategies. The six themes highlighting key life stressors in this second study were similar to those reported by the PI in the first study.(Jones et al., 2016) Two new sources of stress also emerged: social media and life imbalance.(H. J. Jones et al., 2018) Stress-reduction strategies were also similar between the two studies and included exercise, prayer, hobbies and other self-care activities, and fellowship.(H. J. Jones et al., 2018) The 'Strong Black Woman' theme was prevalent in the Cincinnati cohort:

"...we fail to seek assistance...sometimes you have to step back and recognize you might be a little bit in over your head and you need some help"

The focus group discussions in this second study generated ideas for the content (i.e., finances, parenting) and delivery (i.e., lectures, demonstrations) of a culturally tailored stress reduction program. The women also recommended the use of technology (social media, websites) for continued access to information and support. A manuscript authored by the PI and her primary mentor that highlights the ideas for content and delivery of the B-SWELL intervention is under peer review.

The findings for these preliminary studies are notable for their similarities. Midlife Black women in the San Francisco Bay area shared similar experiences with stress and sources of stress with midlife Black women from the Midwest.(Jones et al., 2016; H. J. Jones et al., 2018) Furthermore, the women reported similarities in preferred coping strategies.(Jones et al., 2016; H. J. Jones et al., 2018) The stress reduction strategies reported reflect culturally acceptable approaches for midlife Black women. This preliminary research underscores the importance of using the voices of midlife Black women to inform the design of interventions intended to improve behavior. CBPR methodology will facilitate the collaboration between the research team and the targeted population. This proposed research aims to fill that gap in the current intervention literature; themes identified in the PI's preliminary research(Jones et al., 2016; H. J. Jones et al., 2016; H. J. Jones et al., 2018) will inform the development of a stress-reduction wellness program for midlife Black women, B-SWELL. This project has the potential to improve our knowledge about the complex relationship between stress and behavior while decreasing CVD risk in a high-risk population.

The work of the mentoring team is essential to the success of this research. The primary mentor, [name], has a body of research that focuses on the care of the family caregiver. She developed the Telephone Assessment and Skill-building Kit (TASK) for stroke family caregivers through a K01 Award, then tested efficacy of this innovative program (TASK II) through an R01-funded randomized controlled clinical trial (RCT). (Bakas et al., 2015; Bakas et al., 2009) She has a currently funded R21 designed to optimize the TASK III program using technology (i.e., Task III website and eBook) and goal setting strategies to further improve caregiver health. [name] has invited the PI to join her R21 research team where she will take an active role in helping to optimize the TASK III program. The PI will learn essential skills as a member of [name] research team (i.e., intervention development, clinical trial management, use of technology for intervention delivery). Many midlife Black women serve in caregiving roles, making her involvement in [name] research highly relevant to the current project.

[name] has a body of research grounded in CBPR and the health of under-represented communities.⁶⁴ She is the faculty liaison for the community research advisory board identified in this study and has a currently funded NIH R25 SEPA grant. Her expertise in epidemiology is an excellent complement to this research, as she understands the intersectionality of environment, person, and health; stress-related illness; and the challenges facing midlife Black women. The PI served as a co-investigator on [name] recent research that used recreational music making to decrease stress in midlife Black women.

3.3 Provide the scientific or scholarly background for, rationale for, and significance of the research based on the existing literature and how will it add to existing knowledge.

3.3.1. Cardiovascular Health Disparities for Midlife Black Women.

Black women are projected to have the lowest life expectancy of all racial/ethnic groups in the U.S. by 2060. This lower life expectancy projection is attributed to health problems that occur across the life span but in midlife Black women (ages 40-64), is commonly attributed to cardiovascular disease (CVD). It is estimated that 49% of adult black women have heart disease and over 40% have been diagnosed with hypertension.1 African American women are more likely to be obese, increasing their risk for Type 2 diabetes, hypertension and CVD.29 Although CVD is the number one cause of death in all women, African American women over the age of 60 have the greatest incidence of heart failure30 and 64% of Black women do not know that heart disease is their greatest health risk.1 Despite these statistics, studies show that intervention in midlife can aide in the prevention of chronic conditions like CVD and increase life expectancy.31,32

Midlife Black women are exposed to multiple and competing daily stressors resulting from role changes, major life events, and menopause, in addition to microaggressions and discriminatory acts related to their age,

gender, and ethnicity. The unique stressors experienced by midlife Black women contribute to the development of chronic conditions such as CVD because they tend to occur persistently and over prolonged periods of time. This chronic exposure has been associated with inflammation and plaque development in the vasculature 33. These stressors also function as barriers to the adoption of lifestyle behaviors that can prevent and even reverse these conditions 34. Coping with multiple stressors requires time that could otherwise be devoted to exercise, preparation of healthy foods, sleep, or fellowship; behaviors that have been shown to minimize, and possibly reverse, the effects of chronic stress 6,35. In fact, recent literature supports the need for tailored interventions for midlife Black women based upon observed health disparities and the strong relationship between health deterioration and chronic active coping 13,36

3.3.2. Theoretical underpinnings

In the effort to conceptualize and design a stress-reduction wellness intervention for midlife Black women, two theoretical frameworks will be used: Black Feminist Thought and Social Cognitive theory. Black Feminist Thought is a theoretical point of view that seeks to clarify the ideas and experiences of Black women from the perspective of Black women.37 Black Feminist Thought and its related constructs explain the elevated health risks and morbidity within the context of racism, sexism, and gendered expectations experienced by midlife Black women.10,11 The "Strong Black Woman" is a cultural construct arising from the Black Feminist perspective and was a major theme identified in the PI's preliminary work.8,37 The 'Strong Black Woman' persona, encapsulates a set of characteristics, beliefs, and behaviors that have been historically associated with the 'Strong Black Woman' (independence, resilience, perseverance) and deemed necessary for survival. This persona also contributes to a deterioration of health12 as women struggle to meet the expectations and needs of others with little regard for their own needs.29

Bandura's Social Cognitive Theory39 will guide the development of this intervention. Self-efficacy, a construct arising from Bandura's theory, has been shown to influence the adoption of healthy lifestyle behaviors.40,41 Self-efficacy is defined as "an individual's judgement of his or her capabilities to organize and execute courses of action."42 Self-efficacy recognizes that the intersectionality between person, behavior, and environment is key to understanding the motivations, perceptions, and barriers that influence decisions and the adoption of healthy lifestyle behaviors.39,42 In understanding and recognizing the significant stressors in the lives of midlife Black women, we can make steps to change perceptions and behaviors For this research study, self-efficacy will be viewed as a mediator for the adoption of healthy lifestyle behaviors.

3.3.3. Intervention Research Studies:

Targeting Interventions to Black Women: In general, intervention studies designed to improve healthy lifestyle behaviors are not focused on Black women. However, recommendations on how to tailor and target this population exist.29,43 Interventions targeted to vulnerable populations such as midlife Black women are advised to incorporate theory and take into account cultural and social factors that influence the decision to adopt (or avoid) specific behaviors.44 Mwenda et al. used the 'Transtheoretical Model' stages of change to evaluate factors associated with increased physical activity in a sample of hypertensive Black women.45 In another study, researchers concluded that the inclusion of social networks and a variety of behavioral strategies is imperative when designing interventions intended to improve the adoption of healthy lifestyle behaviors in Black women.46 Social networks, in particular, are key cultural factors of importance to midlife Black women. Finally, a literature review of interventions to promote exercise in Black women recommended that intragroup differences and communal resources be assessed in the design and implementation of interventions.47 The results of these highlighted studies can be applied to future interventions.

Interventions to Improve Health: Intervention studies focused on healthy lifestyle behaviors in Black women tend to target specific health behaviors such as cancer screening or exercise. Few target general health or well-being.50,51 Napholz developed a psychoeducational intervention for Black working women with the goal of reducing role conflict and improving well-being.50 This research focused solely on work role experiences for Black women. Napholz acknowledged the work role as a major life domain and discussed the

impact of prejudicial racial attitudes and other harmful stimuli encountered during daily work place interactions.50 She proposed that gender- and culture-appropriate content improved the receptivity of her intervention and she advocated for the use of tailoring to improve interventions. Work stress was a significant stressor in the preliminary research focus group study conducted by the PI. The proposed research will look beyond work stress to include the multiple, competing stressors experienced by midlife Black women.

Gaston, Porter, & Thomas 52 created an intervention designed to improve knowledge about major illness and nutrition for midlife Black women. This intervention used a support group approach to increase awareness and engagement. In another study, civic engagement was used to promote participation in lifestyle behaviors that reduce CVD risk. The adapted intervention was conducted in churches and 'change clubs' were formed. The 'change clubs' created a social network and group dynamic centered on improving lifestyle behaviors. Both studies aimed to improve general health. Culturally relevant approaches were identified but specific risk factors (i.e. stress) were not addressed.

Stress Interventions: Stress-reduction intervention studies aimed at Black women have targeted health problems such as pre-term labor, high blood pressure, and obesity. These health problems have demonstrated strong associations with stress and alarming disparities for Black women. In a study by Wesley,56 on-to-one sessions using deep breathing exercises or guided imagery were successful in decreasing perceived stress scores in pregnant Black women. Another study by Lechner and colleagues,57 used cognitive behavioral stress therapy to improve psychological adaptation in a sample of Black female breast cancer survivors. Alternatively, Cox and colleagues did not find significant success in their stress-augmented weight loss intervention program for adult Black women.55 Engagement was a key mediator related to lack of adherence to the intervention55 and is often proposed as a rationale for gender and cultural tailoring. These studies demonstrate a willingness of Black women to use a variety of stress-reduction strategies and highlights the importance of culture and inclusion when delivering interventions. No intervention studies were found that focus on the life stressors relevant to midlife Black women and the mechanisms through which these stressors serve as barriers to health lifestyle behavior.

3.3.4. Technology Use During COVID-19 Pandemic.

There has been a steady increase in the use of technology in behavioral interventions. The addition of technology has shown effectiveness in several areas that increase its popularity. Technology has potential to reach a wider scope of people, ease access to information, decrease barriers to participation, improve collection and retention of research data, and eliminate internal bias, among others. Technology used for information and communication in behavioral interventions has been shown to improve outcomes when combined with other methodologies such as face-to-face (Lau, Lau, Wong, & Ransdell, 2011). Several systematic reviews focus on the use of technology in interventions designed to assess the effectiveness of physical activity and/or dietary behavior change. In the majority of systematic reviews (Kroeze, Werkman, & Brug, 2006; Lau et al., 2011; van den Berg, Schoones, & Vliet Vlieland, 2007; Vandelanotte, Spathonis, Eakin, & Owen, 2007), positive effects were noted with the addition of technology while others reported mixed results (Norman et al., 2007). Due to the COVID-19 pandemic, the B-SWELL RCT will be conducted remotely online. The use of technology in this study has the potential to improve our knowledge about technology in behavioral research studies.

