Tablets will be programmed with content and links relevant to the B-SWELL study and appropriate restrictions. Programming will be conducted by the B-SWELL research team under guidance of UC CATER staff. All study materials, including tablets, will be handled in accordance with UC COVID-19 protocols (i.e. gloves and masks).

• All drugs and devices used in the research and the purpose of their use, and their regulatory approval status.

N/A

• The source records that will be used to collect data about subjects. (Attach all surveys, scripts, and data collection forms.)

All study data and tracking will be entered into an electronic data system, REDCap (www.REDCap.org), a secure research electronic data management system with validated data entry, audit trails for tracking data manipulation, and export procedures. It is HIPAA complaint satisfying all local, state, and federal regulation for the capture and storage of private health information for research purposes.

Zoom accounts have been purchased by the UC CON. Zoom accounts will be supported by the UC CON CATER technology experts. Zoom links have been determined to be secure and appropriate for research by the UC depart of research. Members of the B-SWELL research team will be trained in the use and management of online Zoom group sessions, privacy, and technical issues.

The surveys used to collect data are included in the chart below and attached.

Construct	Survey Tool	Time	Baseline	8wks	12wks
Moderators	Demographic data: income, marital status, children, education, health problems, and community of residence (among others).	5	Х		
Mediator	Cohen's Perceived Stress Scale (PSS-10): measures perception of general stress. Items are rated on a scale of $0-4$ (Max score =40). ^{66,67} Higher stress levels correspond with higher scores.	5	X	Х	X
Mediator	General Self-Efficacy Scale (GSE): 10-item psychometric scale that assesses optimistic self-beliefs to cope with life demands ^{.68}	5	Х	Х	Х
Primary Outcome	AHA Life's Simple 7 (LS7): developed to promote cardiovascular health in accordance with the organization's 2020 Impact Goals. ⁶⁹ Risk behaviors scored 0 to 2. Higher scores indicate trend towards optimal health behaviors and lower risk for CVD.	5	X	X	X
Secondary Outcome	Number of Unhealthy Days (UD): Number of days in past month participant felt physical/mental health was not good. ⁷⁰	2	Х	Х	Х

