17.0 Data Management* and Confidentiality

17.1 Describe the data analysis plan, including any statistical procedures or power analysis.

In Aim 1 and Aim 2a, numerical measures will be summarized using descriptive statistics (i.e., means, standard deviations, and frequencies) regarding expert ratings of degrees of accuracy, relevance and feasibility of new components of the B-SWELL program (Aim 1), and recruitment, retention, treatment fidelity ratings, and satisfaction ratings (Aim 2a). For Aims 2b and 2c, numerical dependent variables (stress, self-efficacy, LS7 scores, unhealthy days, perceived general health, depressive symptoms) will be inspected of empirical distributions to ensure they meet conditions for parametric statistical models. Variable transformation will be used otherwise. All statistical tests will be performed using SPSS Version 25. Parameter estimates with P-values less than .05 will be considered statistically significant. Assumptions related to each statistical test used will be checked using residual plots, qq-plots, and tests for homogeneity of variance/ covariance. In Aim 2b, continuous mediators (stress, self-efficacy) will be compared between groups (B-SWELL vs WE) using t-tests at each visit (baseline, 8 weeks, 12 weeks).

In Aim 2c, using mixed effect models, primary (i.e., LS7 summary scores) and secondary outcome measures (i.e., unhealthy days, perceived general health, depressive symptoms) will be assessed for their associations with time (baseline, 8 weeks, 12 weeks), group (B-SWELL vs. WE), and interaction. In particular, each of the outcome measures will be treated as the dependent variable, and the time effect, group effect, and the interaction will be treated as independent variables or fixed effects of interest in the mixed effect model. Random effects will be used to account for within person correlation due to repeated measurements. Other covariates, such as demographics and attendance rate, will be controlled for by including them in the model and checking for their interaction with the intervention. Post hoc analysis of group means will be compared cross-sectionally, as well as longitudinally between time points (such as week 8 or 12 vs. baseline). Considering the limited sample size for this pilot-type of study, statistical tests will not be adjusted for multiple comparisons in post hoc analyses. Significant findings will be considered preliminary in nature and inspire future research.

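### Stress and self-efficacy are labelled mediators, but section 17.1 pre-specifies only unadjusted between-arm t-tests for them and no analysis that links them to LS7

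*Combined protocol and SAP*

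**What the plan says.** The mediator label appears in four places in the combined protocol and SAP.

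- Section 3.3.2, for self-efficacy only: "For this research study, self-efficacy will be viewed as a mediator for the adoption of healthy lifestyle behaviors".
- Section 2.1, Aim 2b, for both constructs: "Compare mediator measures (stress, self-efficacy) for participants in the B-SWELL intervention group with those in the WE group at 8 and 12 weeks".
- The instrument table in section 6 lists the PSS-10 and the GSE under the construct Mediator, and LS7 as the primary outcome. All three are measured at baseline, 8 weeks and 12 weeks.
- Section 17.1, Aim 2b: "continuous mediators (stress, self-efficacy) will be compared between groups (B-SWELL vs WE) using t-tests at each visit".

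For LS7 and the secondary outcomes, 17.1 (Aim 2c) says that "the time effect, group effect, and the interaction will be treated as independent variables or fixed effects of interest in the mixed effect model". Demographics and attendance are given as examples of further covariates; stress and self-efficacy are not. The hypothesis in section 2.2 is a comparison with the control group: that B-SWELL "participants will show improved self-efficacy in managing life stress and adopting the LS7 behaviors". The power paragraph in 17.1 covers comparisons of means only.

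**The concern.** A mediator role rests on two links: the intervention moves the mediator, and the mediator moves the outcome. The plan estimates the first. Nothing in 17.1 puts a mediator into an LS7 model, relates its change to change in LS7, or defines an indirect effect.

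The mechanism is a large part of the study's rationale, and the pilot is meant to support a larger trial. As written, the analysis would report whether stress and self-efficacy differ between arms and whether LS7 differs between arms. It would give no estimate, even a rough one, of whether the two are connected. The one link that is analysed also uses an unadjusted t-test, although a baseline value of each mediator is available.

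**Working it through.** **1. The plan's own power figures.** Inputs from 17.1: 25 per group, two-sided 0.05, effect sizes 0.87 (two-group) and 0.63 (paired).

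- Two-group: noncentrality = 0.87 × √(25/2) = 3.076, critical t (48 df) = 2.011, power 85.4%.
- Paired: noncentrality = 0.63 × √25 = 3.15, critical t (24 df) = 2.064, power 85.6%.

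Both reproduce the stated 85%. Neither concerns a mediator-to-LS7 slope.

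**2. What is estimated.**

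| Link | Analysis in 17.1 |
|---|---|
| Arm → mediator | Unadjusted t-test at each visit |
| Arm → LS7 | Mixed model: time, group, interaction |
| Mediator → LS7 | None |
| Indirect effect | None |

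**3. Gain from baseline adjustment of the first link.** The documents give no effect size expected for the mediators and no correlation over time. Assume an arm effect of 0.5 SD and a baseline-to-week-8 correlation r. The adjusted residual SD is √(1 − r²), so the effect in residual SD units is 0.5/√(1 − r²), and the noncentrality is that value × √12.5.

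| r | Residual SD | Effect | Noncentrality | Power |
|---|---|---|---|---|
| unadjusted | 1.000 | 0.500 | 1.768 | 41% |
| 0.4 | 0.917 | 0.546 | 1.929 | 47% |
| 0.6 | 0.800 | 0.625 | 2.210 | 58% |
| 0.8 | 0.600 | 0.833 | 2.946 | 82% |

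**4. What an added mediator-to-LS7 regression could show.** Simulation, 3,000 trials per row, 25 per arm, complete data. Assumed: correlation 0.6 for both measures, and an arm effect of 0.5 SD on the week-8 mediator. Path a is the arm effect on the week-8 mediator adjusted for its baseline. Path b is the slope of week-12 LS7 on the week-8 mediator, adjusted for arm, baseline mediator and baseline LS7. The indirect effect is a × b. Its 95% interval was found by Monte Carlo draws from the two estimates, as a quick stand-in for a bootstrap.

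| Assumed truth | Mean slope b | Slope significant | Mean indirect effect | Interval excludes zero |
|---|---|---|---|---|
| Full mediation, slope 0.5 | 0.50 | 96% | 0.25 | 56% |
| Full mediation, slope 0.3 | 0.30 | 54% | 0.15 | 28% |
| No mediation, residual correlation 0.5 | 0.50 | 96% | 0.25 | 56% |
| No mediation, residual correlation 0.3 | 0.30 | 56% | 0.15 | 31% |

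In the last two rows LS7 has a direct arm effect of 0.25 SD, and an unmeasured factor produces the residual correlation between mediator and LS7.

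Rows one and three agree for an algebraic reason. With slope 0.5 and mediator residual SD 0.8, the mediator contributes 0.5 × 0.8 = 0.4 to an LS7 residual SD of 0.8, a residual correlation of 0.4/0.8 = 0.5. The arm effect on LS7 is 0.5 × 0.5 = 0.25 in both. The two situations therefore generate the same data distribution, and no regression on these variables can tell them apart.

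**5. Wider range.** Without baseline adjustment, requiring both paths to be significant at 0.05 with N = 50 gives power from 2% (arm effect 0.3 SD, mediator–LS7 partial correlation 0.1) to 83% (0.87 SD and 0.5). At 0.5 SD it runs from 4% to 40% for partial correlations of 0.1 to 0.5. All these inputs are assumptions.

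**The case against.** The strongest defence is that the plan delivers what it promises. Aim 2b undertakes only to compare the two measures between arms, 17.1 does so, and the hypothesis in 2.2 contains no indirect effect. The sentence in 3.3.2 is theoretical background. Section 17.1 calls significant findings preliminary, puts the emphasis on trends, and leaves efficacy to a later trial. Checking first that the intervention moves its intended mediators is a sensible pilot step, and a powered mediation test is not realistic at N = 50. All of this stands, and it keeps the point minor. It does not supply the missing link: the label is used in four places with no analysis behind it.

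Three stronger readings are tempting and are not supported.

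- A reader might infer that the trial itself cannot address mediation. The limit lies in the written analysis: both mediators and LS7 are collected at all three visits. Section 8.1 anticipates secondary analyses but does not specify them, so it softens the gap without closing it.
- A reader might infer that parallel differences in self-efficacy and LS7 will be presented as mediation. Nothing in the documents says so, and the preliminary framing in 17.1 points the other way.
- A reader might infer that one added regression would separate mediation from no mediation. Step 4 shows that it does so only if unmeasured mediator–outcome confounding is assumed away.

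**Conclusion.** The point holds as a minor one. Stress and self-efficacy are called mediators, and 17.1 pre-specifies nothing that relates them to LS7. That conclusion rests on the text alone.

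The size of the remedy depends on assumed values. At 0.5 SD and correlation 0.6, baseline adjustment lifts power for the arm-to-mediator contrast from about 41% to 58% (47% to 82% for correlations of 0.4 to 0.8). At slope 0.5 the mediator-to-LS7 slope would be found in about 95% of trials, but the indirect-effect interval would exclude zero in only about 56%, and in about 30% at slope 0.3. A residual correlation of 0.5 with no mediation gives the same results as slope 0.5. The added estimate would therefore help in planning the larger trial and could not establish mediation in this one. No error rate, sample size or safety matter is affected.

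**What to change.** In section 17.1:

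1. For Aim 2b, replace the unadjusted week-8 t-test on each mediator with an arm contrast adjusted for that mediator's baseline value, reported with a 95% interval.
2. Add, for each mediator, an exploratory regression of week-12 LS7 on the week-8 mediator, arm, baseline mediator and baseline LS7. Report the mediator slope and the indirect effect (the product of the two paths) with bootstrap 95% intervals and no significance claim. State that the mediator is not randomised, so the slope may reflect confounding rather than mediation.

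If the second analysis is not wanted, call the two measures proposed mediators or proximal outcomes throughout, and reword the sentence in 3.3.2 to match.

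The cost is one paragraph in 17.1 and a few lines of code, with no new data collection. The drawback is wide intervals and a slope open to confounding, so the exploratory label has to be carried into the report.
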